**Section B: Questions About Asthma**

**Important note for the study site: If on a previous questionnaire, the parent/caregiver indicated that the child has been diagnosed with asthma, please proceed to Section C.**

Please remind the parent/caregiver that the date of last interview was:

\_\_/\_\_/\_\_\_\_ (DD/MM/YYYY)

**1. Since the last study site visit/telephone call, has the child been diagnosed with asthma by a doctor or health care provider?**

No

Yes

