**TIME AND EVENTS SCHEDULE**

Study Period	Entry Visit a,b	Assessment Period b				
	Months	0	3 (±7 days)	6 (±7 days)	12 (±7 days)	18 (±7 days)
Screening/Administrative						
Informed consent	X					
Eligibility criteria	X					
Baseline demographics c	X					
Medical and family history c,d	X					
Wheezing and medication parent/caregiver card distribution and verification e,f	X	X	X	X	X	X
Clinical Evaluations						
Clinician questionnaire g	X	X	X	X	X	X
	Monthly telephone calls between study site visits h					
Collection of data from lung function tests and allergy tests (immunoglobulin E and skin tests) i			X			
Medical resource utilization j			X			
Medication l			X			
Safety Evaluations						
Serious/reportable adverse events k			X			

- a. The entry visit needs to take place within 3 months after randomization in Study 64041575RSV2004. The last visit of Study 64041575RSV2004 (ie, Day 28) may be used as the entry visit for this study.
- b. Assessments will be performed during study site visits (entry visit and 3, 6, 12, 18, and 24 months after entry visit in Study64041575RSV2002) and during monthly telephone calls with the parent/caregiver between study site visits.
- c. Baseline demographics and medical/family history from the previous Phase 2 Study 64041575RSV2004 will be captured in the long-term follow-up electronic case report form (eCRF).
- d. Medical and family history to identify risk factors for wheezing/asthma at baseline, including prenatal smoking by the subject's mother, subject's exposure to tobacco smoke, wheezing associated with symptoms of acute respiratory infections, whether the subject has siblings or attends kindergarten/day care, and personal and/or family history of atopy/allergy will be recorded in the eCRF.
- e. Parents/caregivers will be provided with a wheezing parent/caregiver card to be completed daily. The information recorded on the wheezing parent/caregiver card will aid the site responsible person to complete the clinical questionnaire when interviewing the subject's parent/caregiver. Parents/caregivers will be required to return the completed parent/caregiver cards to the study sites every 3 months (eg, in person or by mail/email/fax when no study site visit is scheduled).

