#### 9.1.2. Entry Visit

Screening can be performed as soon as it is confirmed that the subject participated in Study 64041575RSV2004 and completed the planned course of the study drug and the last study-related visit. Subjects may be enrolled within 3 months after randomization in Study 64041575RSV2004. The last visit of Study 64041575RSV2004 (ie, Day 28) may be combined with the entry visit of this LTFU study (Study 64041575RSV2002).

At the entry visit, after signing the ICF, the overall eligibility of the subject to participate in the study will be assessed.

Baseline demographics and medical/family history from the previous Phase 2 Study 64041575RSV2004 will be captured in the LTFU (Study 64041575RSV2002) eCRF. Medical and family history to identify risk factors for wheezing/asthma at baseline, including prenatal smoking by the subject's mother, subject's exposure to tobacco smoke, wheezing associated with symptoms of acute respiratory infections, whether the subject has siblings or attends kindergarten/day care, and personal and/or family history of atopy/allergy will be recorded in the eCRF.

Parents/caregivers will be provided with the medication and wheezing parent/caregiver cards, both of which need to be completed on a daily basis (see [Attachment 3](#) and [Attachment 4](#)).

During the entry visit, a clinical questionnaire (see [Attachment 2](#)) needs to be completed by a study site responsible person, by interviewing the subject's parent/caregiver, to collect the following information:

- Wheezing.
- Diagnosis of asthma, eczema, and allergic rhinitis. All medical information needed to confirm the diagnosis of asthma, eczema, and allergic rhinitis needs to be collected by the study site personnel.
- Impact of the subject's health status on normal daily activities for subjects, parents/caregivers, and other family members.

This questionnaire will capture information since the last study visit:

- If the entry visit of Study 64041575RSV2002 coincides with the last visit of Study 64041575RSV2004 (ie, Day 28), the "last study visit" in the questionnaire refers to

the Day 14 visit in Study 64041575RSV2004. Any recalled events in the questionnaire will be related to this time period.

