- If the entry visit of Study 64041575RSV2002 takes place after the last visit of Study 64041575RSV2004 (ie, Day 28), the “last study visit” in the questionnaire refers to the Day 28 visit in Study 64041575RSV2004. Any recalled events in the questionnaire will be in the last 30 days or less (if the entry visit to last study visit of Study 64041575RSV2004 is less than 30 days).

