**a. When was the child diagnosed with asthma by a doctor or health care provider?**

Date of asthma diagnosis: \_\_/\_\_/\_\_\_\_ (DD/MM/YYYY)

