5. EFFICACY

5.1. Primary Efficacy Endpoint(s)

5.1.1. Definition

The primary endpoints are:

1. Clinical diagnosis of asthma within the first 2 years after the RSV infection, as diagnosed by a physician and reported by the parent/caregiver. This will be derived based on the completed study questionnaires at each visit/telephone call until the final visit. It is either “Yes” or “No”.
2. The percentage of wheezing days in a subject within the first 2 years after the RSV infection will be calculated as:

$$\text{Percentage of wheezing days} = \left(\frac{\text{number of wheezing days}}{\text{day of study completion} - \text{day of informed consent} + 1} \right) * 100$$

The percentage will be rounded to the nearest integer. Number of wheezing days is the sum of all days that were reported in the Monthly visit reports. The day of informed consent is the informed consent of the RSV2002 study.

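### The primary asthma endpoint covers two years from the RSV infection, but the questionnaires it is derived from start later and run past two years, and the recorded diagnosis date is not used

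*Protocol*

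**What the plan says.** The endpoint in SAP 5.1.1 is "Clinical diagnosis of asthma within the first 2 years after the RSV infection", as made by a physician and reported by the parent or caregiver. The same section derives it as Yes or No from the questionnaires completed at each visit or call up to the last one.

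Section B of the questionnaire (Protocol Attachment 2) asks: "Since the last study site visit/telephone call, has the child been diagnosed with asthma by a doctor or health care provider". A Yes leads to a date item: "When was the child diagnosed with asthma by a doctor or health care provider". The skip instruction is "If on a previous questionnaire, the parent/caregiver indicated that the child has been diagnosed with asthma, please proceed to Section C", so only a Yes given earlier in this study is carried forward. No item asks whether the child has ever had the diagnosis.

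Protocol 9.1.2 sets the look-back at entry: "This questionnaire will capture information since the last study visit". If entry coincides with Day 28 of the parent study, the reference point is "the Day 14 visit in Study 64041575RSV2004". If entry is later, the reference point is Day 28 and a limit is added: "Any recalled events in the questionnaire will be in the last 30 days or less". The Time and Events Schedule, footnote a, gives the latest entry: "The entry visit needs to take place within 3 months after randomization in Study 64041575RSV2004". Protocol 9.1.3 places the last site visit 24 months after entry.

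The only analysis set is All Enrolled (SAP 2.3.1). SAP 2.4 gives the enrolment as 7 children.

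**The concern.** The endpoint's window and its data source have different limits. The window opens at the RSV infection and closes two years later. The questionnaires open at or shortly before entry to the follow-up study and close about two years after entry. SAP 5.1.1 has no rule to reconcile the two, although the form records the date that would do so.

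This allows two errors in a primary endpoint. A diagnosis made after the infection but before the entry look-back may never be asked about, and so may be missed. A diagnosis made after two years but before the final visit may be counted.

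A separate matter is a child with asthma before the RSV infection. Not counting that child as a new case is correct. However, the SAP neither identifies such children nor lists earlier asthma among its baseline characteristics, so a reader of the proportion cannot tell how many were already diagnosed.

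**Working it through.** The plan states no figure for this point, so there is nothing to reproduce. The steps below set the questionnaire coverage against the endpoint window.

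**Inputs**
- Entry look-back: Day 14 or Day 28 of the parent study, with a 30-day limit in the second case (Protocol 9.1.2).
- Earliest entry: about Day 28, because inclusion criterion 1 requires the last parent-study visit.
- Latest entry: 3 months after randomization (footnote a). I take this as Day 91; the calendar range is 89 to 92.
- Last site visit: entry + 24 months (Protocol 9.1.3).
- Endpoint window: 2 × 365 = 730 days.

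Counts may shift by one day depending on how day numbers are assigned.

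**Start of coverage**

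For entry on Day 28, coverage starts on Day 14. For later entry on day E, it starts on max(28, E − 30). The limit binds only when E − 30 > 28, that is, when E > 58.

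| Entry day | Coverage starts | Unasked days after Day 28 |
|---|---|---|
| 28 (combined) | Day 14 | 0 |
| 29 to 58 | Day 28 | 0 |
| 75 | 75 − 30 = Day 45 | 45 − 28 = 17 |
| 91 | 91 − 30 = Day 61 | 61 − 28 = 33 |

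With the latest entry taken as Day 89 or Day 92, the last figure is 31 or 34. The unasked days before Day 28 (or before Day 14 with combined entry) fall within the parent study.

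**End of coverage**

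Under the protocol schedule, the final visit falls about E + 730 days after randomization. The excess over 730 is therefore E itself: about 28 days for combined entry and 91 days for the latest entry (3 + 24 = 27 months). The visit window allows a further 7 days. This end affects every child followed to the last visit; the gap at the start affects only those entering after Day 58.

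**Whether another source fills the gap**
- The date item in Section B is completed only after a Yes, so it cannot recover a diagnosis that was not asked about.
- Parent-study medical and family history goes into the follow-up eCRF (Protocol 9.1.2).
- Parent-study adverse events still ongoing at entry become medical history (Protocol 12.1.1).
- Adverse event collection in this study starts at consent (Protocol 12.2.1). A diagnosis between Day 28 and a late entry would therefore rest on the history taken at entry or on medical records.
- SAP 5.1.1 refers to none of these sources.

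**What one child does to the result**

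The Wilson 95% interval (SAP 5.1.3), with z = 1.96, has centre (p + z²/2n)/(1 + z²/n) and half-width z√(p(1 − p)/n + z²/4n²)/(1 + z²/n). For all 7 children pooled, with assumed counts:
- 0/7 = 0% (0 to 35.4)
- 1/7 = 14.3% (2.6 to 51.3)
- 0/6, if one child had earlier asthma and is set aside = 0% (0 to 39.0)

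The SAP reports by treatment group, but the documents do not give the split of the 7. In a group of n children, one reclassified child moves the proportion by 1/n.

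**The case against.** Much of the opposing case stands.

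**Earlier asthma may be recorded elsewhere.** A reader might infer that a diagnosis outside the look-back is lost to the study. The documents do not support that: history, ongoing parent-study events and confirmatory records all reach the study file. The questionnaire is the source named for the endpoint, not the only record.

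**The gap is a worst case.** A reader might take all 61 days before the look-back of a Day 91 entry as unobserved, which is 61/730 = 8.4% of the window. But 28 of those days lie inside the parent study, which had its own visits and adverse event reporting. That leaves about 33, and only for the latest entry. Actual entry dates are not given.

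**Scoring as No is inferred.** The SAP does not say how an unasked period is scored. The date item is unrestricted, so a parent could volunteer an earlier diagnosis.

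**The two-year limit is still in the definition.** The phrase about the final visit may only say which questionnaires are read. SAP 1.2 also counts the visits from randomization, which would put the last one at 24 months; the protocol counts them from entry. The late over-count is therefore possible rather than prescribed. What stands is that no rule applies the date.

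**The denominator is prespecified.** A reader might infer that children with earlier asthma must be removed. That would change the quantity estimated. The effect is also modest: at the planned size of 35% × 120 = 42 on lumicitabine, with an assumed 4 cases, removing 1 to 3 children moves 4/42 = 9.5% to between 4/41 = 9.8% and 4/39 = 10.3%, well inside the interval of 3.8 to 22.1.

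**The analysis is small and descriptive.** There are 7 children, nothing is tested and the project was stopped. This limits the consequence but does not remove the mismatch.

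**Conclusion.** The point holds as a mismatch between the primary endpoint's stated window and its derivation. At the start, up to about 33 days after the parent study go unasked, for entry after Day 58 only. At the end, questionnaires may run about 28 to 91 days past two years under the protocol's schedule. Followed as written, SAP 5.1.1 would probably miss a diagnosis in the first period and could count one in the second.

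This rests on three assumptions: 3 months is about 91 days, visits follow the protocol's schedule from entry, and parents answer the question as worded.

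A reader might go further and conclude that the reported incidence is wrong, or that it is biased between groups. The documents do not support either. They give no asthma counts, entry dates or earlier diagnoses for any of the 7 children, and the look-back rule is the same for both treatment groups. The correction is still worth making: this is a primary endpoint, one child out of 7 is 14.3 percentage points, and the information needed is largely collected already.

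**What to change.** In SAP 5.1.1, derive the asthma endpoint from the diagnosis date:

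1. State an origin date. Randomization in Study 64041575RSV2004 is a workable proxy for the RSV infection. The SAP's own symptom-duration categories before randomization run to 5 days, so the proxy should be named as such.
2. Take the diagnosis date from the questionnaire. For the period not asked about, use medical history, parent-study adverse events and collected medical records.
3. Score Yes only if the date is 0 to 730 days after the origin. Do not count later diagnoses; they can be listed.
4. Identify and list children diagnosed before the RSV infection. Keep All Enrolled as the main denominator, and show the proportion among children without earlier asthma as a supplementary result.

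The cost is a few lines of derivation and a record review for 7 children. Records may be incomplete for a child whose parent never reported asthma, and the report should say so. Rewording the entry question to ask about any diagnosis to date would close the gap at source, but the SAP already reports enrolment in the past tense, so it is probably too late for this study.

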**a. When was the child diagnosed with asthma by a doctor or health care provider?**

Date of asthma diagnosis: \_\_/\_\_/\_\_\_\_ (DD/MM/YYYY)

**Section C: Questions About Eczema**

**Important note for the study site: If on a previous questionnaire, the parent/caregiver indicated that the child has been diagnosed with eczema, please proceed to Section D.**

Definition of eczema: dry, itchy, scaly patches on the skin

Please remind the parent/caregiver that the date of last interview was:

\_\_/\_\_/\_\_\_\_ (DD/MM/YYYY)

**1. Since the last study site visit/telephone call, has the child been diagnosed with eczema by a doctor or health care provider?**

No

Yes

**a. When was the child diagnosed with eczema by a doctor or health care provider?**

Date of eczema diagnosis: \_\_/\_\_/\_\_\_\_ (DD/MM/YYYY)

**Section D: Questions About Allergic Rhinitis**

**Important note for the study site: If on a previous questionnaire, the parent/caregiver indicated that the child has been diagnosed with allergic rhinitis, please proceed to Section E.**

Definition of allergic rhinitis: inflammation of the nasal passages due to allergies and characterized by episodes of sneezing, stuffy nose, often accompanied by itching of the eyes and nose.

Please remind the parent/caregiver that the date of last interview was:

\_\_\_/\_\_\_/\_\_\_ (DD/MM/YYYY)

**1. Since the last study site visit/telephone call, has the child been diagnosed with allergic rhinitis by a doctor or health care provider?**

No

Yes 

**a. When was the child diagnosed with allergic rhinitis by a doctor or health care provider?**

Date of allergic rhinitis diagnosis: \_\_\_/\_\_\_/\_\_\_ (DD/MM/YYYY)

### Section E: Questions of the Impact of the Child's Health on the Parent/Caregiver and Family

#### 1. Is the parent/caregiver currently in paid employment?

No 

a. Is the parent/caregiver currently not employed because of the child's health problems?

No

Yes

Yes 

a. Since the date of the last study site visit/telephone call, how many days did the parent/caregiver miss from work because of the child's health problems?

Total number of days missed from work because of the child's health problems:  
 \_\_\_\_\_ days

b. Since the date of the last study site visit/telephone call, how much did the child's health problems affect the ability of the parent/caregiver to be productive on the job (eg, complete tasks on time, get to work on time, pay attention when at work)? If your child's health, affected work only a little, instruct the parent/caregiver to choose a low number. Please circle a number below based on the response from parent/caregiver.

Child's health had  
no effect on  
parent's/caregiver's  
work productivity

0 1 2 3 4 5 6 7 8 9 10

Child's health  
completely prevented  
the parent/caregiver  
from being productive at  
work

2. Since the date of the last study site visit/telephone call, how much has the child's health problems affected the parent's/caregiver's availability to perform normal daily activities (other than work for pay)? By normal daily activities we mean the usual activities you perform, such as working around the house, gardening, shopping, childcare, exercising, studying, etc. If the child's health problem affected activities only a little, instruct the parent/caregiver to choose a low number. Please circle a number below based on the response from parent/caregiver.

Child's health had  
no effect on  
parent's/caregiver's  
normal daily  
activities

0 1 2 3 4 5 6 7 8 9 10

Child's health  
completely prevented  
parent/caregiver from  
doing normal daily  
activities

- 3. Since the date of the last study site visit/telephone call, how much has the child's health affected the child's usual activities? If the child's health had little effect on the child's usual activities, instruct the patient/caregiver to choose a low number. Please circle a number below based on the response from parent/caregiver.**

Child's health had no effect on the child's usual activities	
 
 0	1	2	3	4	5	6	7	8	9	10	
 
	0	1	2	3	4	5	6	7	8	9	10	Child's health severely limited the child's usual activities
0	1	2	3	4	5	6	7	8	9	10			

- 4. Since the date of the last study site visit/telephone call, how much has the child's health affected the parent's/caregiver's health? If the child's health problem had little effect on the parent's/caregiver's health, instruct the patient/caregiver to choose a low number. Please circle a number below based on the response from parent/caregiver.**

Child's health had no effect on the parent's/caregiver's health	
 
 0	1	2	3	4	5	6	7	8	9	10	
 
	0	1	2	3	4	5	6	7	8	9	10	Child's health caused severe health problems for the parent/caregiver
0	1	2	3	4	5	6	7	8	9	10			

- 5. Since the date of the last study site visit/telephone call, has the child's health made it difficult for the caregiver to care for other family members?**

- No  
 Yes

- 6. Since the date of the last study site visit/telephone call, how often did the child's health limit the amount of time the parent/caregiver spent with other family members?**

- Rarely or never limited time  
 Occasionally limited time  
 Often limited time  
 Most of the time or always limited time

- 7. Since the date of the last study site visit/telephone call, how many days did other family members miss from work because of the child's health problems (eg, to stay home to care for the child or other family members, to take time off to take the child for medical visits, etc.)?**

Total number of days that family members missed from work because of the child's health problems: \_\_\_\_ days

**General Reminders for the Parent/Caregiver for the Next Study Site Visit/Telephone Call**

- Please remind the parent/caregiver to bring all medications and medication card to the scheduled study site visits and telephone calls in order to be able to capture the medication history.
- Please remind the parent/caregiver to bring the wheezing card to the scheduled study site visits and telephone calls in order to be able to capture the days of wheezing.
- Please remind the parent/caregiver to bring the wheezing and medication card every 3 months to the site according to local procedures (eg, by mail, by scan/email, in person, etc.).

**End of questionnaire**

**Attachment 3: Wheezing Parent/Caregiver Card to Be Completed Daily****FRONT**

Wheezing card for: \_\_\_\_\_ (name of the child)

January 2018						
Monday	Tuesday	Wednesday	Thursday	Friday	Saturday	Sunday
1	2	3	4	5	6	7
8	9	10	11	12	13	14
15	16	17	18	19	20	21
22	23	24	25	26	27	28
29	30	31				

**BACK****How to use the wheezing card**

- This card is to help you remember which days your child had wheezing; that is a day when you heard whistling sounds in the child's chest during breathing.
- Each day at bedtime:
  - If the child had wheezing that day, put a "1" in the box for the date.
  - If the child did not have wheezing that day, put a "0" in the box for the date.

**How to read the wheezing card during the phone calls with the study coordinator**

- Provide the days the child had wheezing since the last study site visit/phone call.
- Provide the days the child had no wheezing since the last study site visit/phone call.

**Please bring all wheezing cards with you to the study site visits/phone calls! Please also bring the wheezing cards every 3 months to the study site according to local procedures (eg, by mail, by scan/email, in person, etc.)!**

**In case of questions about the study or the wheezing card, please call:**

- Name: \_\_\_\_\_
- Phone number: \_\_\_\_\_

**BACK****How to use the medication card**

- Write all medications prescribed to your child
- For each medication, you need to include the medication name (generic name), indication, route, dose, strength, frequency, start date and stop date.
  - The indication represents the reason for treatment (for example wheezing, asthma, eczema, allergic rhinitis, headache, etc.).
  - The route represents the way the medication is administered to your child (for example oral, inhaled [administered by mask], topical [applied on skin], etc.).
  - The dose represents the number of pills, capsules, puffs, milliliter, teaspoons, tablespoons, etc. that your child has to take every time the medication is given to your child (for example, 2 pills, 5 milliliters, 1 teaspoon).
  - The strength represents the amount (for example, how many mg) per pill, capsule, milliliter, etc. (for example, 20 mg pill, or 15 mg per milliliter).
  - The frequency represents how often the medication is to be given to your child (for example, every 8 hours, every 12 hours, once a day, etc.).
  - The start date represents the date when the first dose was given to your child.
  - The stop date represents the date when the last dose was given to your child.
- Use one medication card per calendar month.
  - If your child has been prescribed many medications in a given month, please use the necessary number of medication cards in order to collect all the medications.

**Please bring all medications and all medication cards with you to the study site visits/phone calls! Please also bring the medication cards every 3 months to the study site according to local procedures (eg, by mail, by scan/email, in person, etc.) !**

